powered however for a 12-month comparison which it is anticipated would come from comparisons of collections made initially at 0 vs 12 months, but with additional comparisons (subject to study continuation) at 6 vs 18 months etc. We base calculations on a current base resistance marker frequency (the Cyp6 gene-cluster marker haplotype described above) of 0.72, which is based on recent local data we have obtained. A projected 5% annual decrease in the PBO arm and 5% increase in the standard LLIN arm, translates into a projected difference between arms of approximately 10% per year. The total number of *An. gambiae* required per collection period to detect such a difference as significant (using an exact test) is N=1392 (allowing a two-fold higher collections in standard-LLIN houses than PBO-LLIN houses). Clustering is not accounted for in the analysis because we postulate (based on general patterns for the species) that it is unlikely there will be significant *a priori* population genetic structure within the *An. gambiae* population of Sud Ubangi.

Allowing for 16% non-*An. gambiae* in collections (based on our data from neighbouring Nord Ubangi province; Lynd et al. 2018) equates to a total of 1,650 Anopheles per survey period. Allowing for an average catch of N=3 *An. gambiae* per standard-LLIN house, and 1.5 in PBO LLIN houses this would require a total number of N=734 houses to be sampled by prokopack collections during each collection around the 6 month periods. We will sample from 4 clusters per arm to reduce travel costs and time). Specifically, we will sample from 3 separate health zones per arm and then from both PBO- and standard-LLIN clusters within the mixed Boto health zone. Villages to be sampled will be those in close proximity to the health centres included in the epidemiological component of the study.

It is intended that the same houses would be sampled each time, though if this is not possible, or if verbal consent to access to sample is not provided a neighbouring replacement house would be recruited. The projected 10% decrease is annual and therefore the main comparisons would compare surveys separated by 12 months, i.e. months 0 vs 12, 6 vs 18, 12 vs 24, etc.

Secondary entomological outcomes

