The primary entomological outcome measure will be the frequency of the molecular deltamethrin resistance marker haplotype. A single species (An. gambiae) is predominant in the study area. Anopheles gambiae typically show limited genetic differentiation even over large spatial scales (Miles et al 2017) and it unlikely that initial marker frequencies will show spatial variation, as noted above. Therefore analysis is planned for an inter-arm comparison using an exact test procedure. However, we will also examine whether spatial autocorrelation is present and introduce a spatial component into analysis using a generalised linear model if this is the case. Other important entomological outcomes (below) include the abundance of mosquitoes. The first secondary entomological outcome – abundance of female malaria vector mosquitoes, which is likely to show much higher variance even at local scales will be analysed using a Poisson generalised linear model with negative binomial link function to determine whether a difference in the density per house between study arms is present annually (i.e. from two 6 monthly collections pooled). Similar analysis will be performed for a measure of the malaria transmission rate – the entomological inoculation rate, which is estimated as the mean number of sporozoiteinfected mosquitoes per house per night, adjusted for the number of sleepers per house (identified from household questionnaire data), again based on the two 6 monthly collections pooled.

Key secondary entomological indicators (all to be measured biannually from the same collections)

Abundance of female Anopheles malaria-vector mosquitoes

Counted from the prokopak collections. Power calculations from the study design above suggest that detection of an annual 50% decrease in *Anopheles* abundance can be detected with >80% power.

Blood feeding rate of female Anopheles malaria-vector mosquitoes

From assessment of the bloodfed status of the above mosquitoes, coupled with limited random molecular testing of mosquito blood meals to quantify the human bloodmeal index.

Sporozoite rate in female Anopheles malaria-vector mosquitoes

Assessed from the same mosquitoes using molecular analysis of the head and thoraces of the females to determine the proportion infective.

Entomological inoculation rate

The number of infective bites/person/night calculated from preceding parameters and the number of sleepers in the house (obtained from questionnaire)

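### The primary entomological contrast is stated in two ways: 1,392 mosquitoes per survey are sized for a between-arm test at one survey, yet the power is attached to month 0 versus month 12 comparisons and a 10% decrease that no arm is projected to show

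*Protocol*

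**What the plan says.** All references are to the Protocol, Entomological part.

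- **Hypothesis and endpoint (Primary).** Marker frequency is expected to be lower in PBO zones than in standard-net zones, through stasis or a fall in the former. The endpoint is a comparative annual frequency.
- **Sample size calculation and power, effect.** The base frequency is that of "the Cyp6 gene-cluster marker haplotype described above) of 0.72, which is based on recent local data we have obtained". From that starting value the two arms are assumed to move apart: "A projected 5% annual decrease in the PBO arm and 5% increase in the standard LLIN arm". The section turns this into a gap of about 10% a year between the arms.
- **Same section, number.** The total "required per collection period to detect such a difference as significant (using an exact test) is N=1392". Twice as many mosquitoes are expected from the standard-net houses as from the PBO houses.
- **Same section, timing.** The work is described as powered for a 12-month comparison, expected to come from "comparisons of collections made initially at 0 vs 12 months", with later pairs such as 6 versus 18 months. The section closes: "The projected 10% decrease is annual and therefore the main comparisons would compare surveys separated by 12 months".
- **Data analysis.** On the ground that initial frequencies are unlikely to vary spatially, "analysis is planned for an inter-arm comparison using an exact test procedure".

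**The concern.** The sample size section describes one effect in two ways. It first builds 10% as the distance between two arms moving 5% in opposite directions. It then calls the same 10% a decrease and uses it to justify comparing surveys 12 months apart. The data analysis section plans a comparison between arms and gives a reason for needing no baseline term.

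These are different contrasts. A between-arm test at month 12 uses one survey. A comparison of month 0 with month 12 is either a change within one arm, where the projected effect is only 5%, or a difference in changes between arms, which adds the sampling error of the month 0 survey. The protocol does not say whether month 0 data enter the primary test. Someone writing the detailed analysis could follow either section, and the 80% power belongs to only one of them. This is the primary entomological hypothesis.

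**Working it through.** **Inputs**

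- Base frequency 0.72, equal in both arms at month 0 (sample size section).
- Effect of 5% down and 5% up. Relative reading: 0.72 × 0.95 = 0.684 and 0.72 × 1.05 = 0.756. The gap is 0.072, or 7.2 points, and 0.072 / 0.72 = 10%. Absolute reading: 0.67 and 0.77.
- Allocation 2:1, so 1,392 / 3 = 464 PBO and 928 standard.
- Alpha and power are not stated for this calculation. I assume two-sided 0.05 and 80%; the epidemiological calculation uses 0.05 and 80% without stating sidedness.
- No allowance for clustering, as in the protocol. Any clustering would lower every power below.

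**Step 1: reproduce 1,392.** Exact power of a two-sided Fisher test, 2:1 allocation, 0.684 against 0.756:

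- 463 + 926 = 1,389: 79.98%
- 464 + 928 = 1,392: 80.04%

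So 1,392 is the smallest 2:1 total that reaches 80%. The absolute reading needs only about 700 to 745 in total and has 97% power at 1,392, so it does not reproduce the figure.

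**Step 2: change within one arm, month 0 to month 12 (Fisher, same numbers at both surveys).**

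- PBO, 464 against 464, 0.72 to 0.684: 20%
- Standard, 928 against 928, 0.72 to 0.756: 40%
- PBO with a literal relative 10% fall, 0.72 to 0.648: 63%. The protocol does not project this.

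**Step 3: difference in changes (normal approximation).** Power = Φ(0.072 / SE − 1.96), where SE² is the sum of p(1 − p)/n over the four arm-by-survey samples.

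- Month 0: 0.2016/464 + 0.2016/928 = 0.000652
- Month 12: 0.2161/464 + 0.1845/928 = 0.000665
- SE = √0.001316 = 0.0363; 0.072/0.0363 − 1.96 = 0.02; power 51%

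Before the nets act, both arms might yield the standard catch of 3 per house. With 734 / 2 = 367 houses per arm that is 1,101 per arm at month 0. Then SE² = 2 × 0.2016/1,101 + 0.000665 = 0.001031, SE = 0.0321, and power is 61%.

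**Step 4: size needed for 80% on the difference in changes.** PBO n per survey = (1.96 + 0.8416)² × [0.2016 + 0.2161 + (0.2016 + 0.1845)/2] / 0.072² = 925, so 3 × 925 = 2,775 mosquitoes per survey, about twice 1,392. The within-PBO contrast would need about 2,533 PBO mosquitoes per survey.

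**Step 5: sensitivity, at 464/928 per survey.**

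| Reading | Between arms, month 12 | Difference in changes | Within PBO | Within standard |
|---|---|---|---|---|
| Relative, one count per mosquito | 80% | 51% | 20% | 40% |
| Relative, two alleles per mosquito | about 98% | about 80% | about 40% | about 70% |
| Absolute points, one count per mosquito | 97% | 79% | 35% | 68% |

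**The case against.** The strongest reply is that the contrast is between arms almost everywhere it is described: in the hypothesis, the endpoint, the derivation of the 10% and the data analysis section. The planned test is the sized test, with its 80%. No section prescribes a within-arm significance test. On this view the closing sentence only explains why 12 months is the relevant interval although collections are six-monthly.

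Most of this stands. A reader might infer that the trial's main entomological test has only 20% to 60% power, or that the choice of test is left open until the data are in. The document does not support either. The data analysis section names both the contrast and the exact test, so those figures belong to an alternative reading.

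The interval-only reading does not clear the text completely. The section ties its power to paired surveys, and a between-arm test at month 12 needs no month 0 partner. The later pairs point the same way. At the stated annual rates the gap between arms at month 24 would exceed the one-year gap, so only a change over 12 months keeps the effect at its annual size. Calling the effect a 10% decrease is wrong on either reading.

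The second reply concerns counting. The endpoint is a haplotype frequency in a diploid mosquito. With two alleles counted, the difference in changes has about 80% power, and its requirement of 2,775 becomes 2,775 / 2, or about 1,388 mosquitoes, close to 1,392. That reading cannot be excluded from the number alone. However, the section gives its figure as a count of mosquitoes for a difference between arms by an exact test, and that calculation matches 1,392 exactly.

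A further inference to avoid is that low power under mere stasis in the PBO arm supports this point. That concerns a smaller effect under the sized test and is a separate question.

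**Conclusion.** The sample size and data analysis sections need reconciling on the primary entomological contrast. The figure of 1,392 supports a between-arm test at one survey, 0.684 against 0.756, with 80% power. It should not be presented as powering comparisons of month 0 with month 12, and the 10% decrease contradicts the section's own projection of 5% down and 5% up.

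The loss of power is conditional. If a change from month 0 were tested, power would be about 51% to 61% for the difference in changes and 20% or 40% within an arm. This rests on relative percentages, one count per mosquito, two-sided alpha 0.05 and no clustering. The difference in changes reaches about 80% only if two alleles per mosquito are counted or the percentages are absolute points, and the absolute-points reading does not reproduce 1,392. If the data analysis section is followed, the planned test keeps its 80% on the protocol's inputs. The point is a wrongly stated property of the design that wording can correct.

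**What to change.** In the entomological sample size section:

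1. Name the difference between arms in marker frequency at month 12 as the primary test, and cross-refer to the data analysis section.
2. Replace the 10% decrease with the assumed frequencies, 0.684 (PBO) against 0.756 (standard), a 7.2-point difference between arms. State alpha, sidedness, power and whether the unit counted is the mosquito or the allele.
3. Label the 0 versus 12, 6 versus 18 and 12 versus 24 month before-after comparisons as descriptive, with their lower power stated.

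If change from month 0 is the intended primary contrast, restate its power on the existing catch instead of saying that 1,392 powers it. Holding 80% would take about 2,775 mosquitoes per survey when each is counted once.

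Items 1 to 3 are wording only and need no extra collections. The cost is a less favourable stated power for the before-after comparisons.

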Sample size calculation and power: From preliminary analyses it was evident that a minimum 8 vs 8 cluster/ arm trial would be required to adequately power the study to detect plausible effect sizes using a relatively simple cluster arm comparison for a single month's data (temporal variation is unknown so it is difficult to include multiple months in *a priori* power analysis). We used fixed assumptions for the number of available health centres/ zone of N=7 and number of ANC1 visitors

per month of N=20, giving a cluster size of N=140. Note that varying the cluster size has only a moderate impact on power, provided health centres are chosen randomly from those available. Parameter values for the inter-cluster coefficient of variation (*k*, which has a large impact on power) were estimated from DHIS2 2018 data from the rate of positive malaria tests per month per capita (i.e. data divided by population size of zone) as a proxy. Following equation 9 in Hayes & Bennett (1999) we calculated k=0.18 from these data. However, noting this is lower than estimated from the only comparable published study from Tanzania (k values of 0.20-0.28 depending on survey round; West et al. 2014) we also examined a 'high COV' value of k=0.3.

Similarly we lacked information on the baseline prevalence of malaria for Sud Ubangi, with the last survey in 2013-14 detecting a rate of 24% in children under 5 (MPSMRM 2013-14), which using a conversion factor of 1.44 between child and pregnant women's prevalences (van Eijk et al. 2015) we used to estimate an ANC prevalence value of 17%, which is also very close to the average figure for the DRC ANCs presented in Hellewell et al. (2018). However, figures in Hellewell vary greatly and thus because of the considerable uncertainty in this point estimate, we examined a range of possible prevalence rates (applicable to the standard-LLIN reference arm).

We identified the minimum detectable reduction in prevalence using equation 4 from Hayes & Bennett (1999) with the following study design parameters:

Arms=2; Clusters (zones)/arm = 8; subjects/ cluster = 140; k = 0.11 or 0.30; α =0.05; power =80%; prevalence in reference standard-LLIN arm (π 0) varied between 5 and 50%

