For the secondary entomological outcome, the density of malaria vector mosquitoes per house, the number of houses to be sampled to provide similar power is much higher, owing to the very high variability expected between houses (based on data from Protopopoff et al. 2018). Therefore, we will pool collections from the 6th and 12th month collection periods (providing a total of N=1468 house collections) to provide adequate power for this analysis to detect a two-fold difference in female *Anopheles gambiae* abundance between study arms (assuming a standard LLIN density of N=3/house).

Power calculations for or other main secondary entomological variable, the entomological inoculation rate, are prone to even higher variance but based on figures from (Protopopoff et al. 2018), the same strategy of pooled assessment from the 6 and 12 month collections as for density assessment should permit detection of the fourfold difference they observed (based on a standard LLIN mean of 1 and coefficient of variation of 6 in each arm).

Logistics: The poor transport network places limitations on feasibility of entomological collections in all zones and we therefore will sample from 4 clusters per arm, choosing those within closer travel distances from Gemena. The collection method proposed is by timed prokopak aspiration (10 min/house), providing a standardised and relatively inexpensive methodology for collecting adult mosquitoes, which can be used for abundance monitoring and infection assessment. In a large study evaluating LLINs in Uganda, aspirator collections have been made in houses (Lynd et al. 2019). Each zone involved will have a collection kit (prokopak, solar charger, batteries, etc) which will be transferred in turn to each of the four collection locations, within each of which we estimate approximately 25 house collections will be required, assuming catch rates of 3/house/collection in standard

Prokopak collection in Tanzania; AIRS 2016

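### Vector density and inoculation rate are to be analysed without any term for cluster or house, and the stated abundance power has no printed house-level or between-cluster variance behind it

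*Protocol*

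**What the plan says.** - **Model.** Under Entomological, Data analysis, the protocol says that female vector abundance "will be analysed using a Poisson generalised linear model with negative binomial link function", to compare density per house between arms with two six-monthly collections pooled. EIR gets a similar analysis, adjusted for sleepers per house. No random effect, robust variance or small-sample correction is named for either outcome.
- **Sample.** Secondary entomological outcomes pools the month 6 and month 12 rounds, "providing a total of N=1468 house collections", to detect a two-fold density difference, "assuming a standard LLIN density of N=3/house".
- **Power, abundance.** Key secondary entomological indicators states that a 50% annual fall in *Anopheles* "abundance can be detected with >80% power".
- **Power, EIR.** The text says only that the same pooling should be enough to detect a fourfold difference, "based on a standard LLIN mean of 1 and coefficient of variation of 6 in each arm". It gives no percentage.
- **Design.** Nets are allocated by health zone, with Boto split. The entomological sample size section takes 3 zones per arm plus the PBO and the standard cluster inside Boto. It adds: "It is intended that the same houses would be sampled each time", with neighbouring replacements where access fails. Logistics describes four collection locations per zone.

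**The concern.** The exposure is assigned to whole zones, so the comparison between arms carries the variation between zones as well as the variation between houses. A model at the level of the single collection sees only the second. It therefore treats differences among a handful of areas as if they were replicated hundreds of times. Repeat visits to a house add a further dependence that the model also ignores.

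This is not a detail left open for a later plan. The protocol states a model, and a statistical analysis plan would have to overrule it. Nor is the matter covered elsewhere. The reason given for not accounting for clustering (no expected population genetic structure) concerns the resistance marker, and so does the conditional spatial term. The mixed model with a small-cluster correction is given for ANC prevalence only. Density is the outcome for which the same section expects much higher variance, even locally.

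At stake are false positive findings on density and EIR, both listed under Key deliverables, and a power statement on which readers may rely when a comparison comes out null.

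**Working it through.** **Inputs from the protocol**
- Density 3 vs 1.5 per house; EIR 1 vs 0.25 with CV 6.
- 734 collections per round. Two rounds give 2 × 734 = 1468, i.e. 734 per arm, or 1468/8 = 183.5 per cluster if spread evenly.
- 4 clusters per arm.

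**Assumptions**
- Two-sided α of 0.05. None is stated for the entomology; the ANC calculation uses "α =0.05; power =80"%.
- House CV for density of 1 to 4. The protocol prints none.
- Between-cluster k. None is given for vectors, so the malaria values are borrowed: 0.18 (estimated from local case data), up to 0.28 (the published comparison) and 0.30 (the high value). The ANC parameter list also prints 0.11 where the text derives 0.18, so 0.11 is shown too.

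**Step 1: house count.** 1650 × (2/3)/3 + 1650 × (1/3)/1.5 = 366.7 + 366.7 = 733.3, hence 734. The figure reproduces.

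**Step 2: power if all collections are independent.** Power = Φ(d/SE − 1.96), with SE² = CV²(μ₀² + μ₁²)/734.
- EIR: SE² = (36 + 2.25)/734 = 0.0521; d/SE = 0.75/0.228 = 3.29; power 91%.
- Density: the stated power cannot be reproduced without a CV. It is 98% at CV 3, 86% at CV 4 and 68% at CV 5, so it exceeds 80% for a CV up to about 4.3.

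**Step 3: add clusters and test on 6 df.** SE² = CV²(μ₀² + μ₁²)/734 + k²(μ₀² + μ₁²)/4, with power from the noncentral t on 8 − 2 = 6 df.

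Example, density with CV 3 and k=0.18: 9 × 11.25/734 + 0.0324 × 11.25/4 = 0.1379 + 0.0911 = 0.2291. SE is 0.479, the noncentrality is 1.5/0.479 = 3.13, and power is 74%.

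| k | Density, CV 1 | CV 2 | CV 3 | CV 4 | EIR, CV 6 |
|---|---|---|---|---|---|
| 0 | 100% | >99% | 92% | 71% | 78% |
| 0.11 | >99% | 98% | 85% | 66% | 76% |
| 0.18 | 97% | 89% | 74% | 58% | 72% |
| 0.28 | 73% | 66% | 56% | 45% | 64% |
| 0.30 | 68% | 61% | 52% | 43% | 62% |

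For EIR, the drop from 91% to 78% at k=0 comes wholly from using a t-test on 6 df in place of a normal test. Between-zone variation accounts only for the further fall.

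**Step 4: type I error of the model without cluster terms.** The variance is understated by the factor 1 + 183.5k²/CV². At CV 3 this is 1.66 for k=0.18 and 2.83 for k=0.30. The actual error is 2[1 − Φ(1.96/√factor)], which gives 12.8% and 24.4%. At k=0.11 it is 7.9%. A simulated single-level negative binomial test (1000 runs, 4 clusters per arm, 184 collections each) rejected in 13.5% and 24.7% of runs at k=0.18 and 0.30 with house CV 3. With house CV 1 it rejected in 37% and 57%.

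**Step 5: repeat houses alone.** With within-house correlation ρ and full overlap, the effective number is 1468/(1 + ρ): 1129 at ρ=0.3 and 979 at ρ=0.5. On the Step 2 basis, EIR power falls to 82% and 77%. This loss is not included in the table, so the table is favourable to the plan in that respect.

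**The case against.** **The power may be right.** This stands in part. The protocol takes its variability from a cited trial and does not print a density CV, so a reader who infers that the abundance power is false goes further than the document allows. At CV 1 or 2 with k=0.18, it stays above 80% under a clustered test, and at k=0.11 it does so even at CV 3. Two things limit this defence. First, the protocol pools two rounds because one is not enough, yet on independent collections one round (367 per arm) already gives 99% at CV 2, 81% at CV 3 and 57% at CV 4. Its own reasoning therefore points to a CV of about 3 or more. Second, a low house CV makes the type I error worse, so the case that rescues the power makes the planned test less valid.

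**The power percentage covers abundance only.** Correct. A reader might carry it over to EIR, but the EIR sentence gives no figure.

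**The model name is only loose wording.** Also correct. A reader might infer that the model cannot be fitted at all. That is too strong: a negative binomial link function exists, though it is an unusual choice, and the phrase almost certainly means negative binomial regression. The wording should be tidied, but the missing terms are the substance.

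**Not every house is visited twice.** True. Revisiting is an intention, with replacements allowed, so the overlap will be large but perhaps not complete.

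**The k values describe malaria, not mosquitoes.** True. The true vector value could be lower or higher.

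**Conclusion.** The analysis as written is wrong for the design. It gives a zone-assigned exposure, sampled in 8 clusters, a model with neither cluster nor house terms. With an assumed house CV of 3, the test would run at about 13% (k=0.18) to 24% (k=0.30) instead of 5%. That direction of error does not depend on the exact k: any variation between clusters inflates it.

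The abundance power is unsupported as printed. Across k of 0.18 to 0.30 and house CV of 1 to 4, it ranges from 97% down to 43% on 6 df. The expectation for EIR rests on independent collections; on 6 df its own inputs give 78% at best and 62% to 72% at k of 0.30 to 0.18.

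The reach is limited to secondary entomological outcomes. Nothing here touches the ANC primary analysis.

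**What to change.** 1. Replace the model wording with a negative binomial mixed model with log link. Include random intercepts for net-type cluster, collection location and house, survey round as a fixed effect, and log(sleepers) as offset for EIR.
2. Define the cluster as the net-type cluster, not the zone. There are 7 zones but 8 clusters, because Boto supplies one to each arm; state how the shared zone is handled.
3. Test the arm effect with a small-sample correction based on the 8 clusters (about 6 df, fewer if Boto is treated as a pair), or compare cluster-level means.
4. Restate the abundance and EIR power as conditional on stated ranges of house CV and k, and print the CV used for density.

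The cost is revised analysis wording and less favourable stated power for secondary outcomes. No additional collections are needed.

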In addition, if sufficient females are available, additional insecticides can be tested on a more limited scale, for example the other major LLIN pyrethroids permethrin and perhaps alpha-cypermethrin or perhaps newer LLIN insecticides such as chlorfenapyr, which if samples of BASF Interceptor G2 were available might be best tested directly in assays on Sud Ubangi mosquitoes.

Net efficacy and lifespan

We need to know when nets start to lose integrity, so that a reduction of impact due to loss of coverage can be distinguished from a reduction of impact due to loss of insecticide. A simple durability monitoring protocol will record holes (and proportionate hole index calculated), coupled with bioassays on the nets, as well as chemical tests done to assess the quantity of deltamethrin and PBO present on the nets. Specifically, bioefficacy will be measured via WHO cone tests using locallycollected mosquitoes (see Figure 9 for collection areas) on sections of LLINs (with separate tests for upper and side panels for Permanet 3) removed from the field (and replaced) at time intervals of 6 months. The LLINs to be removed can be selected randomly from the houses identified for entomological collections above at the end of the mosquito sampling period. Sections of the same LLINs will be tested for active ingredient concentration (with separate tests for upper and side panels for Permanet 3) using HPLC analysis at LSTM. Per collection period we plan to remove an LLIN from a random selection of 10 houses from villages around health centres from 3 zones/arm, giving a total of N=30 LLINs per arm per time point. The 30 LLINs per arm will be tested using one bioassay cone per net for PermaNet 2 (standard) and two for PermaNet 3 (top and side) yielding a total required number of female mosquitoes for testing of N=900. Collections for these would be made at the same time as for insecticide susceptibility tests.

Household recruitment

Mosquito collections

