Following initial contact between the head of each village to be included, randomly identified households (from a GPS list collected during planning for the LLIN distribution by IMA the distribution coordinators) within villages will be visited by study personnel, accompanied by a village resident. If householders are present, the purpose of the study and nature of collections will be explained to them, and if they are willing to be enrolled the head of the household will be asked to sign a consent form the following day, which will give potential permission (subject to verbal consent at the time of collection) to collect from the house on up to 6 occasions at 6 month intervals. If they do not wish to take part, or the head of the household is absent, a neighbouring house will be approached. Owing to the possibility that verbal consents will not be given, or householders may not be present in the property at the time of the collections (between 6am and 10am) we aim to consent

approximately 30% more households than will be sampled, and will call to inform those not included as soon as possible on the collection morning.

LLIN durability

Householder recruitment for quantification of LLIN integrity and removal sampling of LLINs will proceed in the same way as for mosquito collections, albeit on a much smaller scale and involving only a single visit per house. The houses will be different to those included in the mosquito collections and a separate information sheet and consent form will be used.

Additional work of interest but not currently planned or costed for:

Human behavior and malaria risk (highest priority)

The capacity of LLINs to protect is determined by human and mosquito behavior (timing and location of biting). The former can be assessed using simple questionnaires to determine location and sleeping times, and the latter is best assessed using human landing catches (HLCs) conducted indoors and outdoors, recording biting times of mosquitoes (Figure 4), which is quite expensive. If complementary funding became available it would be extremely informative to include this component in the study

Age distribution of the mosquitoes

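### The protocol contradicts itself on whether nets are removed from the mosquito-collection houses; following one of the two passages would put replacement nets into houses re-sampled for density and EIR.

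*Protocol*

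**What the plan says.** Three parts of the Protocol bear on this.

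- **Net efficacy and lifespan.** Nets are "removed from the field (and replaced) at time intervals of 6 months", with 10 houses in each of 3 zones per arm, "giving a total of N=30 LLINs per arm per time point". On their source: "The LLINs to be removed can be selected randomly from the houses identified for entomological collections above", once mosquito sampling for the period has finished.
- **Household recruitment, LLIN durability.** This paragraph covers the same removal sampling. Recruitment proceeds as for mosquito collections, "albeit on a much smaller scale and involving only a single visit per house". On the source: "The houses will be different to those included in the mosquito collections and a separate information sheet and consent form will be used".
- **Entomological sample size calculation and power.** For the mosquito collections, "It is intended that the same houses would be sampled each time", with a neighbouring house as substitute if access fails. The household recruitment section seeks consent for up to six collections, 6 months apart.

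Vector density and EIR are secondary entomological outcomes. Both come from these collections, with months 6 and 12 pooled.

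**The concern.** A house cannot be both on and off the mosquito-collection list. Both statements stand in current text, and neither is marked as replacing the other, so a field team could follow either.

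The choice matters because the collection houses form a repeated series. A net replaced at the end of one round is still in the house at the next. The Protocol's aim is to follow how the nets' entomological efficacy changes over time, and the net efficacy section wants to separate loss of coverage from loss of insecticide. Study-supplied replacement nets in the houses that provide the density and EIR series work against both purposes.

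There is also a consent side. The mosquito-collection consent is described as permission to collect from the house, whereas net removal is given its own information sheet and form. Taking nets from collection houses would need a permission that the recruitment section does not describe for them.

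**Working it through.** **1. The Protocol's own house count.** Inputs from the entomological sample size section: 1,650 *Anopheles* per survey, and average catches of 3 per standard-LLIN house and 1.5 per PBO-LLIN house.

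- 1,650 / (3 + 1.5) = 366.7, rounded up to 367 houses per arm; 2 × 367 = 734, as stated.
- Pooled over months 6 and 12: 2 × 734 = 1,468, as stated.

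The 734 reproduces with equal numbers of houses per arm. The Protocol does not state that split, so it is an assumption below.

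**2. Share of houses given a replacement net per round**, if nets come from collection houses: 30 / 367 = 8.2% per arm. If they come from different houses the share is 0.

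**3. Share of the planned pooled analysis.** Each arm has 2 × 367 = 734 house collections over months 6 and 12. Removal comes at the end of a sampling period, so it affects only later rounds. The Protocol does not say whether the first removal is at month 0 or month 6.

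| First removal | Affected at month 6 | Affected at month 12 | Share of pooled collections |
|---|---|---|---|
| Month 6 | 0 | 30 | 30 / 734 = 4.1% |
| Month 0, different houses each time | 30 | 60 | 90 / 734 = 12.3% |

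**4. Later rounds, if the study continues.** Before a sixth round there are at most five removals.

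- Different houses each time: 5 × 30 / 367 = 150 / 367 = 40.9%.
- Random re-selection: 1 − (1 − 30/367)^5 = 34.7%.

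**5. What such shares could do to the results.** Let *s* be the share of collections after a replacement, and let *x* be the further proportional fall in density in those houses (*x*P in the PBO arm, *x*S in the standard arm). The Protocol gives no value for *x*; 0 to 50% is assumed. With a true PBO/standard density ratio of 0.50, the two-fold difference the study targets, the observed ratio is

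0.50 × (1 − *s*·*x*P) / (1 − *s*·*x*S).

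| *s* | Range of observed ratio | Fall in arm mean density at *x* = 50% |
|---|---|---|
| 4.1% | 0.49 to 0.51 | 0.041 × 0.5 = 2.0% |
| 12.3% | 0.47 to 0.53 | 0.123 × 0.5 = 6.1% |
| 40.9% | 0.40 to 0.63 | 0.409 × 0.5 = 20.4% |

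The ends of each ratio range need the full 50% in one arm and none in the other. Equal proportional falls leave the ratio at 0.50 but still lower the density level. Because *s* grows with each round, they also bend the time trend.

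**The case against.** The strongest reply is that the problem is optional and the safeguard is already written.

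- The net efficacy sentence is permissive: nets can be taken from collection houses. The durability paragraph is firm: the houses will be different.
- The sampling plan later in the net efficacy section speaks only of houses in villages near the health centres, which fits the durability paragraph.
- One net per house is removed, so a household with several nets would not become a house of new nets.
- Neither primary outcome (ANC prevalence, marker frequency) is shown to be affected.

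All of this stands, and it limits the point to a wording conflict with a conditional consequence. It does not remove the conflict.

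One might also read the net efficacy sentence as meaning the roughly 30% extra households consented but not sampled. The text does not say so. That reserve is about 0.3 × 367 = 110 houses per arm, enough for three full rounds of 30 out of a possible six, and the separate-consent conflict would remain.

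A reader might infer more than the documents support:

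- **That the series will be contaminated.** It would be only if the net efficacy sentence were followed.
- **That the relevant share is 16% (60/367), or 22% to 55% within three zones.** The first is the month-12 survey alone, with removals from month 0. The second assumes that the removal zones are three of the four collection clusters, and no density or EIR analysis of that subset is planned. The planned analysis pools months 6 and 12.
- **That sporozoite rates would be clearly distorted.** Infection in a mosquito reflects earlier feeding across the community, and nothing in the Protocol lets one size an effect of one new net in 10 houses per zone.

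**Conclusion.** The contradiction is certain; its consequence depends on which passage is followed. Under the net efficacy sentence, 8.2% of collection houses per arm would receive a replacement net per round. Between 4.1% and 12.3% of house collections in the pooled month 6 and 12 density and EIR data would come after a replacement. The share could reach 41% of houses at a sixth round, if the study runs that long and takes different houses each time.

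These figures assume 367 houses per arm, re-sampling of the same houses as intended, and one net per selected house. The effect on the early between-arm ratio is modest even under one-sided assumptions. The greater harm is to density and EIR levels and to the trend with net age, and it grows with follow-up. The affected outcomes are secondary, but the text should be reconciled before field teams act on it.

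**What to change.** Delete or amend the sentence in the net efficacy and lifespan section so that it agrees with the LLIN durability paragraph: durability nets are drawn at random from houses in the same villages that are not on the mosquito-collection list. The cost is one sentence, since separate recruitment, information sheet and consent are already planned.

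No further rule is needed to drop collection houses whose nets have been renewed. Such a rule has no basis in the Protocol, would cut against its intention to keep the same houses, and could exclude households that renew nets themselves.
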